2.2.6 Protocol Violations/Withdrawals

If a study participant is to be excluded/dropped from the study database and/or analysis, the PIs/coordinators will provide to the statistical analysis team the following: 1) the specific reason for dropout (e.g., withdrawal, protocol violation), in as much detail as possible; 2) who decided that the participant would be excluded; and 3) whether the exclusion involves some or all types of participation.

2.3 Statistical Report Contents

The following section outlines the contents of the final statistical analysis. For all analyses, baseline is defined as the measurement collected during the baseline survey. Subjects who are enrolled in the study and are eligible will be analyzed in the groups to which they were allocated regardless of actual intervention received.

2.3.1 Description of study population

Sample size:

The total number of subjects who are consented/registered and withdrawn will be given. A summary of subjects who were withdrawn will be provided.

Demographics and Clinical Characteristics, Patient and Parent:

Demographic and clinical characteristics as measured at baseline will be summarized by trial arm.

Variables to be summarized are: parent age, parent race and ethnicity, relationship to child, parent sex, parent marital status, parent education, technology use, parent numeracy score, child sex, child age, child race and ethnicity, child insurance. Variables will be summarized using descriptive statistics appropriate for each type of data item.

Baseline characteristics with large differences between groups will be included in analyses evaluating the effectiveness of the intervention.

Practice characteristics:

Practice characteristics measured prior to randomization assignment (start of study) including physician sex, physician race and ethnicity, physician age, years at practice, number of ADHD subjects seen per week will be summarized by trial arm. Variables will be summarized using descriptive statistics appropriate for each type of data item.

2.3.2 Primary outcome analysis

Primary outcome: Medication continuity as measured by number of days covered with medicine within 6 months of medication start.

- Number of days covered with medicine is calculated from audit of prescriptions written during the first 6 months of medication treatment.

For the primary outcome, the dependent variable will be a count of the number of days covered with medicine within 6 months of ADHD medication start date. Differences between intervention and control groups on this outcome will be evaluated using a generalized linear model assuming a Poisson distribution with a log link function. The number of days from start of medication to end of study will be included in the model as an offset. Other potential covariates (e.g. baseline characteristics of child age, and race with large differences between groups) will be included in a secondary analysis model evaluating the effectiveness of the intervention.

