1.2 Outcome measures

Primary

- Medication continuity as measured by number of days covered with medicine within 6 months of medication start.
 - Number of days covered with medicine is calculated from audit of prescriptions written during the first 6 months of treatment.

Secondary

- Proportion with parent entered data to track response to treatment
 - Entered data is defined by completion of at least one parent-completed Vanderbilt (VADPRS) between medication start to 6 months post medication start
- Total number of measures completed by parents to track child response to treatment from date of medication start to 6 months post medication start
 - Measures completed are defined by completion of the Vanderbilt (VADPRS)
- Number of family portal logins from date of registration to 6 months post medication start.

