2.2.3 Completion

Patient will be considered to have completed the study once the patient completes the 6-month post medication survey or study end date on 9/24/17.

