2.2.5 Missing data

We will complete chart audits of prescriptions written to calculate our primary outcome for all study participants unless consent is withdrawn. Our approach for handling missing data will be to first assess consent withdrawal rates and evaluate whether or not the rates are very different between the two arms of the trial. If the rates/reasons are similar, we will perform the analysis assuming *Missing Completely at Random (MCAR)*, i.e., the propensity for a data point to be missing is completely random such that there is no relationship between whether a data point is missing and any values in the data set, missing or observed (missing data are a random subset of the data). If consent withdrawal rates are very different between the two arms of a trial, then our results will be limited by concerns about potential bias.

For secondary outcomes, missing outcome data could occur for several reasons such as item nonresponse, lost to follow-up, and data collection errors. Secondary outcomes are supportive and exploratory in nature, thus we will not impute missing secondary outcomes. Results of secondary outcomes will be limited by potential bias due to missing data.

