2.3.3 Secondary outcome analyses

- Proportion with parent entered data to track response to treatment

The dependent variable will be the proportion with parent entered data to track response to treatment as any Vanderbilts completed by the parent from date of medication start to 6 months post ADHD medication start date. Differences between intervention and control groups on this outcome will be evaluated using a logistic regression model. Potential covariates (e.g. baseline characteristics of age, race, with large differences between groups) will be included in a secondary analysis model evaluating the effectiveness of the intervention.

- Total number of measures completed by parents to track child response to treatment from date of medication start to 6 months post medication start
 - Measures completed are defined by completion of the Vanderbilt (VADPRS)

The dependent variable will be a count of the number of Vanderbilts completed by the parent from date of medication start to 6 months post ADHD medication start date. Differences between intervention and control groups on this outcome will be evaluated using a generalized linear model assuming a Poisson distribution with a log link function. The number of days from start of medication to end of study, 6 months post medication will be included in the model as an offset. Other potential covariates (e.g. baseline characteristics of age, race, with large differences between groups) will be included in a secondary analysis model evaluating the effectiveness of the intervention.

- Number of parent portal logins from registration to 6 months post mediation start

The dependent variable will be a count of the number of portal logins from date of study registration to 6 months post ADHD medication start date. Differences between intervention and control groups on this outcome will be evaluated using a generalized linear model assuming a Poisson distribution with a log link function. The number of days from portal registration to end of study, 6 months post medication will be included in the model as an offset. Other potential covariates (e.g. baseline characteristics of age, race, with large differences between groups) will be included in a secondary analysis model evaluating the effectiveness of the intervention.

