2.3.4 Intervention Fidelity measures

Intervention group only

The following will be summarized as count and percentage:

- Proportion of parents who completed the Shared Decision-Making component
- Proportion of parents who selected an outcome measure (defined as set a behavior to be tracked)
- Proportion of parents who entered monitoring data (defined as filled in behavior rating data)
- Proportion of parents who received text messages
- Proportion of parents who used the social forum (starting 3/6/16)

Associations between parent characteristics and intervention fidelity measures noted above will be evaluated using logistic regression models. Separate models will be utilized for each of the 5 fidelity measures listed above. The following variables will be included as independent variables in the logistic regression models:

- Parent Technology use
 - Measured at baseline and defined by use an app to track or manage health (yes/no)
- Primary Caregiver Parent Education
 - 3 levels: HS or less, some college (2 yr or tech), college grad or above
- Parent Numeracy
 - The Subject Numeracy scale measured at baseline
 - Continuous measure

Associations between the 5 intervention measures listed above and medication continuity (primary outcome) measure will be evaluated using the same approach described under the primary outcome analysis. Separate models will be utilized for each of the 5 fidelity measures listed above.

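### The primary model for days covered fixes the variance by a plain Poisson assumption; at an assumed mean of 120 and SD of 20–60 days, a nominal 5% error becomes about 28–72%.

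*SAP*

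**What the plan says.** Section 2.3.2 of the SAP defines the primary analysis: "the dependent variable will be a count of the number of days covered with medicine within 6 months of ADHD medication start date". Arms are compared with a "generalized linear model assuming a Poisson distribution with a log link function". On follow-up time it adds: "The number of days from start of medication to end of study will be included in the model as an offset".

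Section 1.2 explains how the outcome is built: "Number of days covered with medicine is calculated from audit of prescriptions written during the first 6 months of treatment". Section 2.2.3 lets a participant's time in the study end when the family "completes the 6-month post medication survey or study end date on 9/24/17", so follow-up windows may differ between children.

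Section 2.3.4 relates each of the five fidelity measures to medication continuity in the intervention arm; these associations "will be evaluated using the same approach described under the primary outcome analysis". The primary model is therefore used five more times.

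The SAP names no dispersion parameter, quasi-likelihood, robust variance, alternative distribution or check of the variance assumption. It also states no significance level and no expected mean or SD.

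**The concern.** A Poisson model suits independent events that occur one at a time, for which the variance equals the mean. Days covered is a different kind of quantity. It cannot exceed the child's window, and it moves in blocks of prescribed supply. A child who misses one prescription can lose a whole block of days, and a child who stops early loses all the remaining ones.

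When the real spread between children exceeds what Poisson allows, the estimated rate ratio is unaffected but its standard error is too small. Ordinary variation in prescribing and refilling can then be reported as an effect of the enhanced portal, in either direction, and the confidence interval looks far more precise than 80 children can support. The offset adjusts the expected number of days for follow-up time. It does not relax the link between variance and mean.

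**Working it through.** **Inputs from the SAP.** 80 children planned, 40 per arm, 8 practices (section 1); outcome and model as above. The plan states no power, error rate or variance, so there is no figure of its own to reproduce.

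**Inputs assumed.** Two-sided 5% test; mean 120 days (also 90 and 150); SD 20–60 days; six months taken as 182 days; 30-day prescriptions in the block models; no clustering unless stated. An SD of 60 is feasible: the largest possible SD on 0–182 at mean 120 is √(120 × 62) = 86.

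**1. What the model assumes.** With equal windows the Poisson SD is √mean: √120 ≈ 11 days, and at most √182 ≈ 13.5 days for a full window.

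**2. Effect on the test.** Let φ = SD²/mean. The standard error is too small by √φ, and the true two-sided error is 2 × [1 − Φ(1.96/√φ)], whatever the sample size. The plan's SE of the log rate ratio is √(2/(40 × 120)) = 0.020.

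| SD (mean 120) | φ | √φ | Correct SE | True error |
|---|---|---|---|---|
| 20 | 3.3 | 1.8 | 0.037 | 28% |
| 30 | 7.5 | 2.7 | 0.056 | 47% |
| 45 | 16.9 | 4.1 | 0.084 | 63% |
| 60 | 30.0 | 5.5 | 0.112 | 72% |

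At mean 150, SD 20–60 gives 23–69%; at mean 90, 35–76%. The error passes 50% when φ exceeds (1.96/0.6745)² = 8.44, that is, above an SD of 32 at mean 120 (28 at mean 90, 36 at mean 150). Break-even is SD = √mean; below it the test is conservative (SD 8 at mean 120 gives 0.7%).

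**3. Spread produced by prescriptions alone.** If six 30-day prescriptions are each written independently with probability p, the mean is 180p and the variance 900 × 6 × p(1 − p), so φ = 30(1 − p).

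- p = 0.95, 0.90, 0.80, 0.67: true error 11%, 26%, 42%, 53%. Above p = 0.967, φ falls below 1 and the inflation disappears.
- First prescription always written, then permanent stopping, with monthly continuation 0.98, 0.95, 0.90, 0.80: about 40%, 57%, 66%, 72%.

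**4. Simulation that respects the cap** (beta-distributed coverage rounded to whole days, 80 children). On a full window, SD 20, 30, 45, 60 gave 28%, 47%, 64%, 73% for plain Poisson and about 5% with a Pearson scale.

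**5. Unequal windows with the offset** (uniform 60–182 days, same spread of coverage). Plain Poisson gave 21%, 41%, 58%, 67%; Pearson-scaled gave 5–6%. Here the raw SD²/mean must not be read as φ: a truly Poisson outcome at rate 0.66 with these windows has a raw SD of 25 days yet rejects only 5%. The residual φ was 2.2, 5.0, 11.3 and 20.2.

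**6. Fidelity models** (40 intervention children, split 10/30 or 20/20). SD 20, 45, 60 gave 28%, 63–64%, 72–73%; Pearson-scaled gave 4–5%. An uncorrected sandwich variance gave about 7% at 10/30.

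**7. Clustering, kept apart from the figures above.** At an assumed ICC of 0.05, the Pearson-scaled test still rejects 9–12%. A t test on the 8 practice rates (6 df) rejects about 5%.

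**The case against.** The SAP never says that the dispersion is fixed at 1; that is read from its naming only a Poisson model. An analyst could add a scale, and section 2.1.1 requires departures from the plan to be described and justified. This is true as far as it goes. But the plan followed as written gives the plain Poisson standard error, and a scale added after seeing the data would be an unplanned choice on the primary test.

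The mean, SD, significance level and prescription length are all assumed. Some plausible settings fall below 28%: 11% and 26% with high-probability 30-day prescriptions, 21% with unequal windows, 23% at mean 150 and SD 20. The 28–72% range is therefore illustrative. The condition for inflation is an SD above the square root of the mean. Children who were all partly covered to a similar degree, with an SD near 11 at mean 120, would give about 5%. That uniformity is hard to reconcile with an outcome that moves in supply blocks, and even an SD of 15 gives 15%.

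The 13.5-day ceiling presumes windows capped at six months, whereas the offset in section 2.3.2 runs to the end of study. Reading that as a calendar date does not help: with assumed offsets of 182–600 days the plain Poisson test rejected 57–77%.

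Finally, the SAP describes a pilot. It nonetheless states a directional hypothesis for this outcome in section 1.1 and fixes the model that tests it.

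**Conclusion.** The point holds, and the primary analysis must be corrected. The stated model gives a standard error that is too small whenever the SD of days covered, given the window, exceeds the square root of its mean, about 11 days at a mean of 120. Under the assumptions listed, the true error is about 28–72% for SDs of 20–60 days on a full window. Across the wider set of scenarios it starts at about 11%. The direction is secure unless coverage is very uniform between children; the exact size depends on a mean and SD that the SAP does not give. The same fault carries into the five fidelity–continuity models.

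**What to change.** In section 2.3.2, replace the plain Poisson model with one whose variance is estimated from the data: quasi-Poisson with a Pearson scale or robust variance, or a fractional-logit or quasi-binomial model of days covered over the child's available window. Any of these would serve. State the choice before analysis.

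Carry it into the fidelity–continuity models of section 2.3.4, using the Pearson scale or a small-sample correction where groups are small and uneven.

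Correct the missing practice-level term as well. It is a separate defect, but a scale alone does not bring the trial comparison to its nominal error.

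Lower priority: a scaled Poisson or negative binomial model for the Vanderbilt and login counts in section 2.3.3. On these, section 2.2.5 says: "Secondary outcomes are supportive and exploratory in nature".

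The cost is SAP wording and one model option for dispersion, with no new data. Confidence intervals will be wider, and for the trial comparison they reach the right width only once the practice-level correction is also made.

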Official Title of the study: **Developing New Technologies to Improve ADHD Medication Continuity**

NCT number: **NCT02390791**

Document name: **Analysis Plan**

Date of the document: **11/1/17**

ADHD Enhanced Portal Statistical Analysis Plan

Prepared by: [name]

Date: 11/1/17

Analysis plan approved by:

[name], MEd, MSc
Associate Professor
Division of General and Community Pediatrics
PI ADHD Enhanced Portal Study

11/1/17
Date

The results of the ADHD Enhanced Portal Pilot study Aim 3 will be assessed as described in this document. This statistical analysis plan begins with an overview of the key components of the study including its design, objectives, and outcome measures. This is followed by a detailed description of the statistical analyses that will be utilized to address Aim 3 study hypotheses.

1. Overview of study: This study is a multi-practice, cluster randomized trial to evaluate the effectiveness of an Enhanced ADHD portal. Practices that agree to participate in the study were randomized 1:1 to receive either the intervention (enhanced ADHD portal) or the control group (standard portal) prior to subject enrollment. We used a covariate-constrained randomization procedure to ensure that the intervention and control practices were balanced with respect to: 1) number of health care providers and 2) average percentage of Medicaid patients (Ivers et al. 2012). We planned to enroll a total of 80 children newly diagnosed with ADHD from 8 practices in this trial (40 from the intervention practices and 40 from the control practices).

1.1 Study Objective: Evaluate the general effectiveness of the intervention (e.g. enhanced ADHD portal), compared to control (e.g. standard portal), on medication continuity as measured by prescription records and other more proximal outcomes during the first six months of treatment.

Working hypothesis 1: compared to the control group, the intervention group will have greater medication continuity as measured by number of days covered with medicine.

Working hypothesis 2: compared to the control group, the intervention group will have greater proportion with parent entered data to track response to treatment.

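### Eight practices were randomised, but every outcome model is specified at child level with no allowance for practice, so for any positive within-practice correlation the standard errors are too small and false positives exceed the nominal rate

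*SAP*

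**What the plan says.** Section 1 of the SAP is explicit about the design: "This study is a multi-practice, cluster randomized trial to evaluate the effectiveness of an Enhanced ADHD portal". Practices "were randomized 1:1 to receive either the intervention (enhanced ADHD portal) or the control group (standard portal) prior to subject enrollment". On size it says "We planned to enroll a total of 80 children newly diagnosed with ADHD from 8 practices in this trial", divided as "40 from the intervention practices and 40 from the control practices". Allocation was constrained on two practice-level factors, the number of providers and the average percentage of Medicaid patients.

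The analysis sections are written at child level:

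- **Primary outcome (2.3.2).** Days covered with medicine are "evaluated using a generalized linear model assuming a Poisson distribution with a log link function". The only other term in the main model is the offset: "The number of days from start of medication to end of study will be included in the model as an offset". Child-level baseline characteristics enter in a secondary model only.
- **Binary secondary outcome (2.3.3).** "Differences between intervention and control groups on this outcome will be evaluated using a logistic regression model".
- **Count secondary outcomes (2.3.3).** Completed Vanderbilts and portal logins use the same Poisson model with an offset.
- **Fidelity measures (2.3.4).** Their associations with medication continuity reuse the primary approach, within the intervention arm.

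Practice characteristics are summarised by arm in 2.3.1. Practice does not appear in any model, and neither constraint factor is named as a covariate.

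**The concern.** Treatment varies only between practices. The error of the arm comparison must therefore be judged against the variation between practices in the same arm, of which there are 8 in total. A child-level model judges it against variation between children, as if each child had been randomised separately.

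The two agree only if children in the same practice are no more alike than children in different practices. That is unlikely here. The primary outcome is built from an audit of prescriptions written, which depends on prescribers' habits. Portal use plausibly depends on how a practice promotes the portal.

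If outcomes are correlated within practice, p-values are too small and confidence intervals too narrow. A chance difference between a few practices could then be reported as an effect of the enhanced portal, on the primary outcome and on each secondary outcome.

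**Working it through.** **Inputs from the SAP (Section 1).** 8 practices and 80 children, hence 80/8 = 10 per practice. Allocation 1:1, hence 4 practices and 40 children per arm. The SAP has no power calculation to reproduce.

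**Assumed, because the SAP does not state them.** A two-sided 5% test, and an ICC of 0.01 to 0.10.

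**Formulas, with m = 10.**

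- Design effect: DE = 1 + (m − 1) × ICC
- Factor by which the child-level standard error is too small: √DE
- Effective sample size: 80/DE
- Actual type I error: 2 × [1 − Φ(1.960/√DE)]
- Width of a valid interval relative to the child-level one: (2.447/1.960) × √DE, where 2.447 is the 97.5% point of t on 8 − 2 = 6 degrees of freedom

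| ICC | DE | √DE | Effective N | 1.960/√DE | Type I error | Interval ratio |
|---|---|---|---|---|---|---|
| 0 | 1.00 | 1.00 | 80 | 1.960 | 5.0% | 1.25 |
| 0.01 | 1.09 | 1.04 | 73 | 1.877 | 6.0% | 1.30 |
| 0.05 | 1.45 | 1.20 | 55 | 1.628 | 10.4% | 1.50 |
| 0.10 | 1.90 | 1.38 | 42 | 1.422 | 15.5% | 1.72 |

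The first row separates the two parts of the interval ratio. The move from the normal to t on 6 degrees of freedom gives 2.447/1.960 = 1.25 on its own; clustering supplies the remaining factor √DE.

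**Unequal practice sizes.** With an assumed coefficient of variation of 0.5 in practice size, DE = 1 + [(1 + 0.25) × 10 − 1] × ICC = 1.115, 1.575 and 2.15. The type I error becomes 6.3%, 11.8% and 18.1%.

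**Simulation under no effect.** 20,000 trials per setting, 4 against 4 practices of 10 children, equal follow-up, simple allocation. Assumed: mean days covered 120 and, for the binary outcome, a proportion of 0.4.

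| Analysis | ICC 0.01 | ICC 0.05 | ICC 0.10 |
|---|---|---|---|
| Child-level Poisson, variance equal to the mean | 6.2% | 10.5% | 15.6% |
| Child-level, dispersion-corrected, SD about 24 or 40 | 6.0–6.1% | 10.0–10.2% | 15.5–16.4% |
| Child-level logistic | 6.4% | 10.7% | 16.2% |
| t-test on practice means, 6 df, count outcome | 4.9–5.2% | 4.9–5.2% | 4.8–5.2% |
| t-test on practice proportions, 6 df, binary outcome | 5.6% | 5.4% | 5.3% |

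The simulation agrees with the formula, and the practice-level analysis holds its level approximately.

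**What these rates leave out.** They isolate clustering. The SAP also names no dispersion parameter. With an assumed SD of about 24 or 40 days, the plain Poisson test of the primary outcome rejects 37% or 59% of the time at ICC 0. Overdispersion is a separate defect. The second row of the table shows that correcting it alone leaves the clustering inflation in place.

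**The case against.** The strongest reply is that the SAP is silent rather than wrong. It names a distribution, link, offset and covariates, and says nothing on variance estimation, so a GEE or robust variance is not excluded in so many words. This does not carry the point. The outcome model is what an SAP has to fix, nothing defers it to another document, and an analyst following the text would fit an ordinary GLM. An uncorrected robust variance would not be adequate with 8 clusters in any case.

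Other objections have some force:

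- **The size is conditional.** Neither the ICC nor the significance level is stated. At ICC 0.01 the excess is modest. The direction is fixed for any positive ICC; the size is not known.
- **Allocation was constrained.** If provider numbers and Medicaid share predict the outcome, balancing them removes part of the between-practice imbalance, and the inflation would be somewhat lower than under simple allocation. It does not put a practice-level variance into the model.
- **Six degrees of freedom is not the only valid reference.** Adjusting for both constraint factors would leave 8 − 2 − 2 = 4, and a permutation test over the permitted allocations needs no t distribution.
- **This is a pilot, and the secondary outcomes are called supportive and exploratory.** That softens the point for some secondary outcomes. However, the SAP states directional hypotheses for the primary outcome and for parent-entered data, and tests both between arms.

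**Conclusion.** The concern holds. The design in Section 1 and the models in 2.3.2 and 2.3.3 do not match, and no other section supplies an adjustment for practice. For any positive within-practice correlation, the plan as written gives standard errors that are too small for the primary and all secondary comparisons.

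Assuming 10 children per practice, a two-sided 5% test, simple allocation and an otherwise correct variance, clustering alone takes the type I error from 5% to about 6% at ICC 0.01, 10% at 0.05 and 16% at 0.10. Unequal practice sizes would raise these figures; the constrained allocation may lower them. The correction should be made before the arms are compared.

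**What to change.** In 2.3.2 and 2.3.3, replace the plain Poisson and logistic models with one stated approach that accounts for practice and is suited to 8 clusters. Any of these would serve:

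- a generalised linear mixed model with a random practice intercept and small-sample degrees of freedom (between-within or Kenward-Roger type);
- GEE clustered on practice, with a small-sample-corrected sandwich variance (Kauermann-Carroll or Mancl-DeRouen) and a t reference on 6 degrees of freedom;
- a t-test on practice-level summaries, or a permutation test over the allocations permitted by the constrained randomisation.

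The uncorrected sandwich variance should be ruled out. The SAP should also state the significance level, say whether the two constraint factors are adjusted for (and reduce the degrees of freedom if so), and commit to reporting the estimated ICC. The fidelity models for medication continuity in 2.3.4 inherit the primary approach and should follow the change. A practice term may not restore the nominal level for the count outcomes unless overdispersion is handled as well.

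The cost is SAP wording and a few lines of SAS or R. No new data are needed, since allocation was by practice and each child's practice is known. Intervals will be wider, by roughly 1.3 to 1.7 times over the assumed ICC range on 6 degrees of freedom, and the report should present them as such.
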